1.1 Synopsis

Name of Sponsor: Otsuka Pharmaceutical Co., Ltd

Name of Investigational Medicinal Product: (¹⁴C)-OPC-61815

Protocol No.: 263-102-00006

EudraCT No.: 2019-001968-29

Protocol Title: A Phase I, Open-Label Trial to Assess the Mass Balance and Pharmacokinetics of a Single Intravenous Administration of (¹⁴C)-OPC-61815 to Healthy Male Japanese Subjects

Protocol Lay Person Short Title: A Phase I, Open-Label Trial to Assess the Absorption, Metabolism, and Excretion of (¹⁴C)-OPC-61815 in Healthy Male Japanese Subjects

Clinical Phase/Trial Type: Phase I

Treatment/Indication: Cardiac edema

Objectives and Endpoints:

| Table 1.1-1 Trial Objectives and Endpoints | |
|---|---|
| Objectives | Endpoints |
| 
Primary:
 
To determine the mass balance of total radioactivity following a single intravenous (IV) infusion of (¹⁴C)-OPC-61815.
 
To determine routes and rates of elimination of total radioactivity following a single IV infusion of (¹⁴C)-OPC-61815.
 
To assess the pharmacokinetic (PK) of total radioactivity in plasma and whole blood following a single IV infusion of (¹⁴C)-OPC-61815.
 
To assess the PK of OPC-61815 free form and OPC-41061 in plasma following a single IV infusion of (¹⁴C)-OPC-61815.
 
To identify and characterize metabolites in plasma, urine, and feces following a single IV infusion of (¹⁴C)-OPC-61815.
 | 
The PK parameter endpoints for OPC-61815 free form and OPC-41061 in plasma, and total radioactivity in whole blood and plasma, and the PK parameter endpoints for total radioactivity in urine and feces are detailed in Section 9.4.3.2.
 |
| 
Secondary:
 
To assess the safety and tolerability of a single IV infusion of (¹⁴C)-OPC-61815.
 | 
Metabolic profile of (¹⁴C)-OPC-61815 and identification of radiolabeled metabolites present at >10% of the total drug-related exposure (AUC) plasma.
 
Adverse events, clinical laboratory evaluations, physical examination findings, vital signs (blood
 |

| | |
|--|---|
| | pressure, pulse rate), body weight, and 12-lead electrocardiogram parameters. |
|--|---|

Trial Design:

Single-site, open-label, nonrandomized, single intravenous (IV) dose trial in healthy male Japanese subjects.

Potential subjects will be screened to assess their eligibility to enter the trial within 28 days prior to the dose administration. Subjects will be enrolled and admitted into the trial site on Day -1. On Day 1, all subjects will receive a single IV infusion of 16 mg containing approximately 75.1 μ Ci (2.78 MBq) of (^{14}C)-OPC-61815 infused over 60 minutes (55 to 65 minutes, inclusive) in the fasted state.

Subjects will be confined to the trial site until at least Day 9. Subjects will be discharged from the trial site on Day 9 if the following discharge criteria are met:

- $\geq 90\%$ mass balance recovery, and/or
- $< 1\%$ of the total radioactive dose is recovered in combined excreta (urine and feces) in 2 consecutive 24-hour periods.

If these criteria are not met by Day 9, subjects will remain at the trial site until any one of the discharge criterion are met up to a maximum of Day 10 to continue 24-hour blood, urine, and feces collections for total radioactivity, unless otherwise agreed upon by the sponsor and investigator.

If criteria are not met by Day 10, subjects may be asked to collect 24-hour excreta samples on up to 2 further occasions on a nonresidential basis to allow extrapolation of urinary and fecal excretion. If needed, the 2 additional 24-hour nonresidential collections will start on Days 10 and 11 (to be brought to the trial site at the end of the collection interval on Days 11 and 12, respectively). If on the second occasion the subject has still not met the desired criterion, then the subject will be discharged from the trial, per investigator and sponsor decision.

Trial Population:

It is planned for at least 8 healthy male Japanese subjects to be dosed to ensure that 6 subjects complete the IV infusion. Up to a maximum of 10 subjects will be dosed in total.

Key Inclusion/Exclusion Criteria:

Key inclusion criteria include but are not limited to the following: Male subjects between 35 and 55 years of age, inclusive; hold a valid Japanese passport and be first-generation

Japanese, defined as the subject, the subject's biological parent, and all of the subject's biological grandparents being of exclusive Japanese descent, have been born in Japan, and not lived outside of Japan for more than 5 years; with a body mass index between 18.5 and 28.0 kg/m², inclusive, and a total body weight between 50 and 100 kg, inclusive; in good health, determined by no clinically significant findings from medical history, physical examination, 12-lead electrocardiogram (ECG), vital sign measurements, and clinical laboratory evaluations (congenital nonhemolytic hyperbilirubinemia [eg, suspicion of Gilbert's syndrome based on total and direct bilirubin] is not acceptable) at Screening and Check-in as assessed by the investigator (or designee); and have a history of a minimum of 1 bowel movement per day.

Key exclusion criteria include but are not limited to the following: History of stomach or intestinal surgery or resection that would potentially alter absorption and/or excretion (including cholecystectomy; uncomplicated appendectomy and hernia repair will be allowed); poor peripheral venous access; participation in a clinical trial involving administration of an investigational drug (new chemical entity and/or OPC-61815) in the past 90 days prior to dosing or 5 half-lives of the investigational drug; subjects with exposure to significant diagnostic or therapeutic radiation (eg, serial X-ray, computed tomography scan, barium meal) or current employment in a job requiring radiation exposure monitoring within 12 months prior to Check-in; subjects who have participated in any clinical trial involving a radiolabeled investigational drug within 12 months prior to Check-in.

Trial Site(s): 1 site in the UK

Investigational Medicinal Product(s), Dose, Dosage Regimen, Treatment Duration, Formulation, Mode of Administration:

(¹⁴C)-OPC-61815: Subjects will receive a single IV infusion of 16 mg (¹⁴C)-OPC-61815, containing approximately 75.1 µCi (2.78 MBq), over a period of 60 minutes (55 to 65 minutes, inclusive) on Day 1 of the trial.

Trial Assessments:

Assessments for PK: Blood sampling for OPC-61815 free form and OPC-41061 plasma concentrations, whole blood and plasma total radioactivity, and metabolite profiling and identification (plasma). Urine sampling for total radioactivity and metabolite profiling and identification. Feces sampling for measurement of total radioactivity and where possible, metabolite profiling and identification.

Assessments for Safety: Adverse events, clinical laboratory evaluations, physical examination findings, vital signs (supine blood pressure and pulse rate), body weight, and 12-lead ECG.

Screening/Other: demographics, medical history, prior/concomitant medications, urine drug screen, alcohol breath test, serology, oral body temperature, and height.

Data Monitoring Committee: No

Statistical Methods:

Pharmacokinetic parameters will be summarized using descriptive methodology. The following PK parameter endpoints for OPC-61815 free form and OPC-41061 in plasma and total radioactivity in whole blood and plasma will be calculated using standard noncompartmental methods: area under the concentration-time curve (AUC) from time zero to infinity (AUC_{∞}), AUC calculated to the last observable concentration at time t (AUC_t), maximum peak concentration of the drug (C_{max}), time to maximum peak concentration (t_{max}), time of last measurable (positive) concentration (t_{last}), and terminal-phase elimination half-life ($t_{1/2,z}$). The total body clearance (CL) will also be determined for OPC-61815 free form. The AUC ratios of whole blood total radioactivity relative to plasma total radioactivity (ratios of Blood/Plasma for both AUC_{∞} and AUC_t) will be calculated.

The following PK parameter endpoints for total radioactivity in urine will be calculated: amount excreted in urine (Ae,u), cumulative Ae,u , percentage excreted in urine (% fe,u), and cumulative % fe,u . The following PK parameter endpoints for total radioactivity in feces will be calculated: amount excreted in feces (Ae,f), cumulative Ae,f , percentage excreted in feces (% fe,f), and cumulative % fe,f . Overall amount and percent of total radioactivity in excreta (combined urine and feces) will be calculated.

No formal statistical analysis will be performed.

Trial Duration:

Each subject in this trial is expected to participate in the following periods of the trial (approximate durations listed):

[figure not shown]
- Screening period (27 days; Day -28 to Day -2)
- Check-in (Day -1)
- Treatment period:
 - Dose administration on Day 1
 - Minimum treatment period duration: 9 days (Day 1 to Day 9)

- Maximum treatment period duration: 12 days (Day 1 to Day 12)
- Including an outpatient follow-up for 48 hours, if applicable (at investigator's discretion; Day 10 to Day 12)

Final Discharge from trial will be day of discharge from residential treatment period or the day of last outpatient visit if required to attend them based on the discharge criteria.

The total duration of trial participation for each subject (from Screening through Final Discharge from trial) is anticipated to be a maximum of approximately 40 days.

1.2 Schema

^a Subjects can be discharged on Day 9 if the following discharge criteria are met: $\geq 90\%$ mass balance recovery and/or $< 1\%$ of the total radioactive dose is recovered in combined excreta (urine and feces) in 2 consecutive 24-hour periods. If the discharge criteria are not met, subjects will be asked to remain resident within at the trial site and additional 24-hour collection (blood, urine, and feces) for total radioactivity will continue until these criteria are met, up to a maximum of Day 10.

^b Up to 2 additional 24-hour nonresidential collections (urine and feces) for total radioactivity may occur if discharge criteria have not been met by Day 10. Subjects will collect excreta samples at home for the 24-hour period prior to the clinic visit and deliver them to the trial site at the end of the collection interval, within 24 hours

Figure 1.2-1

Trial Design Schematic

1.3 Schedule of Assessments

| Table 1.3-1 | | Schedule of Assessments | | | | |
|---|-----------------------------------|-------------------------|--|----------------|--|--|
| Period | Screening Day -28 to Day -2 | Check-in Day -1 | Days 1 to 8 | | Discharge ^a Days 9 to 10 | Outpatient Visits ^b Days 11 to 12 |
| ENTRANCE/HISTORY | | | | | | |
| Informed consent | X | | | | | |
| Demographics | X | | | | | |
| Inclusion/Exclusion Criteria | X | X | | | | |
| Medical history | X | X ^c | | | | |
| Urine drug screen | X | X | | | | |
| Alcohol breath test | X | X | | | | |
| Serology | X | | | | | |
| Height and body weight | X ^d | X ^e | 24 and 48 hours after the start of infusion ^e | | | |
| INVESTIGATIONAL MEDICINAL PRODUCT ADMINISTRATION | | | | | | |
| (¹⁴ C)-OPC-61815 | | | Day 1 (0 hours) | | | |
| PHARMACOKINETICS | | | | | | |
| Blood sampling for OPC-61815 free form and OPC-41061 concentration (plasma) | | | Predose and 1 hour (end of infusion), and 1.5, 2, 3, 4, 6, 12, 24, and 48 hours after the start of infusion | | | |
| Blood sampling for total radioactivity (whole blood and plasma) | | | Predose and 1 hour (end of infusion), and 1.5, 2, 3, 4, 6, 12, 24, 48, 72, 96, 120, 144, and 168 hours after the start of infusion | X ^a | | |

Table 1.3-1 Schedule of Assessments

| | | | | | |
|--|---|----------------|---|-------------------|----------------|
| Blood sampling for metabolite profiling and identification (plasma) | | | Predose and 1 hour (end of infusion), and 1.5, 2, 3, 4, 6, 12, 24, 48, 72, 96, 120, 144, and 168 hours after the start of infusion | | |
| Urine collection for total radioactivity and metabolite profiling and identification | | | Predose (from Check-in to 0 hours) and 0 to 24, 24 to 48, 48 to 72, 72 to 96, 96 to 120, 120 to 144, and 144 to 168 hours after the start of infusion | X ^a | X ^b |
| Feces collection for total radioactivity and metabolite profiling and identification | | | Predose (from Check-in to 0 hours) and 0 to 24, 24 to 48, 48 to 72, 72 to 96, 96 to 120, 120 to 144, and 144 to 168 hours after the start of infusion | X ^a | X ^b |
| SAFETY | | | | | |
| Adverse event recording | X | X | Ongoing | X | X |
| Prior/concomitant medication monitoring | X | X | Ongoing | X | X |
| Clinical laboratory evaluations | X | X | 1.5 ⁱ , 24, and 48 hours after start of infusion | X ^g | |
| Physical examination | X | X ^f | 1.5, 24, and 48 hours after start of infusion ^f | X ^{f, h} | |
| Supine blood pressure and pulse rate | X | X | 1.5, 24, and 48 hours after the start of infusion | X ^h | |
| Oral body temperature | X | | | | |
| 12-lead electrocardiogram | X | X | 24 and 48 hours after the start of infusion | X ^g | |

^a Subjects can be discharged on Day 9 if the following discharge criteria are met: $\geq 90\%$ mass balance recovery and/or $< 1\%$ of the total radioactive dose is recovered in combined excreta (urine and feces) in 2 consecutive 24-hour periods. If the discharge criteria are not met, subjects will be asked to remain resident within at the trial site and additional 24-hour collection (blood, urine, and feces) for total radioactivity will continue until these criteria are met, up to a maximum of Day 10.

^b Up to 2 additional 24-hour nonresidential collections (urine and feces) for total radioactivity may occur if discharge criteria have not been met by Day 10. Subjects will collect excreta samples at home for the 24-hour period prior to the clinic visit and deliver them to the trial site at the end of the collection interval, within 24 hours.

^c Interim medical history.

^d Height measured at Screening only.

^e Weight only.

^f Symptom-directed physical examination.

^g Day 9.

^h Only on day of Discharge.

ⁱ At this time point only blood samples will be taken for clinical laboratory evaluation.

| Table 1.3-2 Time Windows for Assessments | | | |
|---|------------|---|--|
| Item | Day | Time point relative to start of infusion (h) | Window |
| Blood sampling for Pharmacokinetics | 1 | predose | Within 2 hours of IMP administration |
| | | 1 | Within 2 minutes after end of IMP administration |
| | | 1.5 | Specified time point \pm 2 minutes |
| | | 2 | Specified time point \pm 3 minutes |
| | | 3 | Specified time point \pm 5 minutes |
| | | 4 | Specified time point \pm 10 minutes |
| | | 6, 12 | Specified time point \pm 15 minutes |
| | 2 | 24 | Specified time point \pm 30 minutes |
| | 3 | 48 | Specified time point \pm 30 minutes |
| | 1 | 1.5 | Specified time point \pm 10 minutes |
| Clinical laboratory evaluations | 2 | 24 | Specified time point \pm 120 minutes |
| | 3 | 48 | Specified time point \pm 120 minutes |
| | 1 | 1.5 | Specified time point \pm 10 minutes |
| Physical examination | 2 | 24 | Specified time point \pm 60 minutes |
| | 3 | 48 | Specified time point \pm 60 minutes |
| | 1 | 1.5 | Specified time point \pm 10 minutes |
| Blood pressure and pulse rate | 2 | 24 | Specified time point \pm 60 minutes |
| | 3 | 48 | Specified time point \pm 60 minutes |
| | 1 | 1.5 | Specified time point \pm 10 minutes |
| Body weight | 2 | 24 | Specified time point \pm 60 minutes |
| | 3 | 48 | Specified time point \pm 60 minutes |
| 12-lead electrocardiogram | 2 | 24 | Specified time point \pm 60 minutes |
| | 3 | 48 | Specified time point \pm 60 minutes |

Abbreviations: h = hour; IMP = investigational medicinal product.

2 Introduction

OPC-61815 is a compound based on the arginine vasopressin V₂-receptor antagonist tolvaptan (OPC-41061 used henceforth). OPC-41061 was developed as an oral aquauretic agent for the treatment of fluid volume overload conditions and has been approved for the indication of hyponatremia in the US and European countries. OPC-61815 is being developed as an injection formulation, which is expected to provide new clinical benefit in the treatment of hyponatremia and various edematous diseases in patients who have difficulty in swallowing or poor absorption of oral medications.

Please refer to the OPC-61815 Investigator's Brochure (IB)¹ for more detailed information.

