
2.4.2 Pharmacokinetics

Pharmacokinetic data for OPC-61815 free form following single and multiple IV doses is presented in the table below. The PK data for OPC-61815 free form following 1- and 5-minute infusions is available in the IB¹, along with PK data for OPC-41061 and major metabolites for all studies.

Table 2.4.2-1 Pharmacokinetic Data for OPC-61815 Free Form

| Dose (mg) | AUC _∞ (ng.h/mL) | AUC _t (ng.h/mL) | C _{max} (ng/mL) | t _{max} (h) ^a | t _{1/2} (h) |
|--|-------------------------------|-------------------------------|-----------------------------|--------------------------------------|-------------------------|
| Single IV dose – Mean (SD) | | | | | |
| 0.3 mg | - | 7.803 (8.170) | 53.02 (29.28) | 0.020 (0-0.25) | - |
| 1 mg | 175.0 (-) | 85.90 (21.91) | 182.2 (21.72) | 0.000 (0-0.25) | 0.7170 (0-0) |
| 3 mg | 427.2 (61.14) | 374.3 (52.91) | 559.5 (85.52) | 0.000 (0-0.02) | 0.6335 (0.1065) |
| 7.5 mg | 1242 (182.2) | 1144 (171.1) | 1832 (294.2) | 0 (0-0) | 1.172 (0.2819) |
| 15 mg | 3008 (416.6) | 2868 (362.3) | 3348 (637.7) | 0.000 (0-0.25) | 1.730 (0.3279) |
| 30 mg | 4882 (817.9) | 4727 (839.9) | 7670 (755.3) | 0 (0-0) | 1.683 (0.4837) |
| Multiple IV dose – Day 1: Mean (SD) | | | | | |
| 1.25 mg | 211.8 (32.11) | 167.3 (32.55) | 371.8 (78.15) | 3.0 (3-3) | 0.5308 (0.1074) |
| 5 mg | 886.7 (140.8) | 784.0 (150.2) | 1165 (394.4) | 3.0 (3-15) | 1.193 (0.3741) |
| 20 mg | 3379 (492.8) | 3178 (400.1) | 4351 (1496) | 3.0 (3-15) | 2.510 (1.927) |
| Multiple IV dose – Day 9: Mean (SD) | | | | | |
| 1.25 mg | 169.0 (33.05) ^b | - | 320.0 (89.42) | 3.0 (3-15) | 0.5748 (0.1549) |
| 5 mg | 924.8 (136.9) ^b | - | 1375 (368.4) | 3.0 (3-3) | 1.329 (0.4530) |
| 20 mg | 3416 (344.7) ^b | - | 4137 (955.7) | 3.0 (3-15) | 2.419 (1.145) |

Abbreviations: AUC_∞ = area under the concentration-time curve from time zero to infinity; AUC_t = area under the concentration-time curve calculated to the last observable concentration at time t; AUC_{24h} = area under the concentration-time curve from time zero until 24 hours postdose; C_{max} = maximum peak concentration; IV = intravenous; t_{max} = time to maximum peak concentration; t_{1/2} = elimination half-life.

^a median (min-max)

^b AUC_{24h}

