4.3 Dosing Rationale

A single dose level of 16 mg, containing approximately 75.1 μ Ci (2.78 MBq) of (^{14}C)-OPC-61815, will be administered to each subject. This equates to a radioactivity exposure of approximately 1 mSv. The radioactive dose is an acceptable dose to give to healthy subjects and is considered adequate to define the disposition of (^{14}C)-OPC-61815.

The committed effective radiation doses to be administered have been calculated by Public Health England's (PHE) Centre for Radiation, Chemical, and Environmental Hazards, based on the results of a preclinical mass balance trial and a quantitative whole body autoradiography trial.⁴ The effective radiation dose is defined as being within dose limits for members of the public (Category II trial, World Health Organization)⁵ with a minor associated risk (risk Category IIa, ICRP).³

In order to provide the optimal conditions for the objectives of the trial to be met, the radioactive dose considered for administration will be reviewed following calculation by PHE, together with any bioanalytical data from the preclinical species to ensure radioactivity concentrations in urine, feces, and plasma are detectable for sufficient periods postdose.

Intravenous administration was chosen since this is the intended clinical route of administration. Based on the nonclinical data and the known PK of OPC-61815, the sample collection timing and duration of this trial are considered adequate to achieve the trial objectives.

A 16-mg dose of (^{14}C)-OPC-61815 is within the anticipated clinical dose range and is considered to be high enough to fully characterize the single IV dose PK of the parent compound.

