6.1 Trial Treatments Administered

Subjects will receive a single IV infusion of 16 mg (¹⁴C)-OPC-61815, containing approximately 75.1 µCi (2.78 MBq), over a period of 60 minutes (55 to 65 minutes, inclusive) on Day 1 of the trial.

Subjects may be asked to be supine for the IV infusion. The subject's start and end time of infusion will be documented in the source data and eCRF. If the infusion is interrupted, the time (start and end of interruption) for each interruption, reason for interruption, if the administration was temporarily suspended and resumed, and if the full dose was administered will be documented in the subject's source documents and eCRF.

Subjects will be dosed in numerical order.

For information regarding the criteria required to be met for subject discharge, see [Section 4.1](#).

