9.4.3.2 Pharmacokinetic Analysis

For the primary objectives, the following PK parameter endpoints for OPC-61815 free form and OPC-41061 in plasma, and total radioactivity in whole blood and plasma will be calculated using standard noncompartmental methods: AUC from time zero to infinity (AUC_{∞}), AUC calculated to the last observable concentration at time t (AUC_t), C_{\max} , time to maximum peak concentration (t_{\max}), time of last measurable (positive) concentration (t_{last}), and terminal-phase elimination half-life ($t_{1/2,z}$). The total body clearance (CL) will also be determined for OPC-61815 free form. In addition, AUC ratios of whole blood total radioactivity relative to plasma total radioactivity (ratios of Blood/Plasma Ratio for both AUC_{∞} and AUC_t) will be calculated. The following PK parameter endpoints for total radioactivity in urine will be calculated: amount excreted in urine (Ae,u), cumulative Ae,u , percentage excreted in urine (% fe,u), and cumulative % fe,u ; and the following PK parameter endpoints for total radioactivity in feces will be calculated: amount excreted in feces (Ae,f), cumulative Ae,f , percentage excreted in feces (% fe,f), and cumulative % fe,f . Overall amount and percent of total radioactivity in excreta (combined urine and feces) will be calculated.

Additional noncompartmental PK parameters may be determined where appropriate.

Pharmacokinetic parameters will be summarized using descriptive methodology. No formal statistical analysis will be performed.

For the primary objective to identify and characterize metabolites in plasma, urine, and feces, the endpoint is the metabolic profile of (¹⁴C)-OPC-61815 and identification of radiolabeled metabolites present at >10% of the total drug-related exposure (AUC) plasma.

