10.3 Appendix 3: Total Blood Volume

The following blood volumes are the maximum that will be withdrawn for each subject.

Table 10.3-1 Total Blood Volume

| | Up to Day 9 (inclusive) ^a | | |
|---|--------------------------------------|---------------------------------|----------------------------|
| | Volume per blood sample (mL) | Maximum number of blood samples | Total amount of blood (mL) |
| Clinical laboratory evaluations | 7.5 | 6 | 45 |
| Serology | 3.5 | 1 | 3.5 |
| Plasma for OPC-61815 free form and OPC-41061 concentrations | 3 | 10 | 30 |
| Whole blood for total radioactivity | 2 | 16 | 32 |
| Plasma for total radioactivity | 5 | 16 | 80 |
| Plasma for metabolite profiling and identification | 10 | 15 | 150 |
| Total | | | 340.5 |

^a Subjects could be discharged on Day 9 if the discharge criteria are met or may be resident within the Clinical Research Unit for an additional 24-hour collection (blood) for total radioactivity up to Day 10.

If extra blood samples are required, the maximum blood volume to be withdrawn per subject will not exceed 500 mL.

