8.5.1.2. Criteria for the Regression Analysis of the Terminal Elimination Phase

- At least 3 data points will be included in the regression analysis and preferably should not include C_{max} .
- When assessing terminal elimination phases, the adjusted coefficient of determination for exponential fit (R^2 -adj) will be used as a measure of the goodness of fit of the data points to the determined line.
- The λ_z will not be assigned if the R^2 -adj value of the regression line is <0.8. In cases where the λ_z is not assigned all regression based parameters (including R^2 -adj) will not be calculated.
- Time period used for the estimation of $t_{1/2,z}$ will be calculated over a time period of at least 2 half-lives (λ_z Span Ratio >2), where possible. Where λ_z Span Ratio <2 the robustness of $t_{1/2,z}$ will be discussed in the CSR.

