8.5.1.3. Calculation of Area Under the Concentration-time Curve

- The minimum requirement for the calculation of AUC will be the inclusion of at least 3 consecutive concentrations above the lower limit of quantification (LLOQ), with at least 1 of these concentrations following C_{max} .
- AUCs will be calculated using the Linear Trapezoidal Linear/Log Interpolation method.

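### With no sample during the 60-minute infusion, AUC∞ of OPC-61815 free form is likely understated and CL overstated; 0.5 h and 8 h samples, added together, largely remove this

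*Protocol*

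**What the plan says.** The dose is given "over a period of 60 minutes (55 to 65 minutes, inclusive) on Day 1 of the trial" (Protocol 6.1). Plasma for OPC-61815 free form and OPC-41061 is drawn at "Predose and 1 hour (end of infusion), and 1.5, 2, 3, 4, 6, 12, 24, and 48 hours after the start of infusion" (Protocol 1.3). There is nothing between predose and the end of infusion, and nothing between 6 and 12 h. Protocol 10.3 counts the same ten samples: "Plasma for OPC-61815 free form and OPC-41061 concentrations | 3 | 10 | 30".

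AUC∞ and terminal half-life are primary endpoints, and "The total body clearance (CL) will also be determined for OPC-61815 free form" (Protocol 9.4.3.2). The dose is "considered to be high enough to fully characterize the single IV dose PK of the parent compound" (Protocol 4.3). The same section calls the sampling times adequate but gives no calculation.

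On analysis, "AUCs will be calculated using the Linear Trapezoidal Linear/Log Interpolation method" (SAP 8.5.1.3). Postdose BLQ values are set to missing (SAP 8.5.1.1). The half-life needs at least three points and, where possible, "will be calculated over a time period of at least 2 half-lives" (SAP 8.5.1.2). No LLOQ is stated in either document.

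**The concern.** During a constant infusion of a drug with fast early disposition, concentration climbs steeply and then flattens. A straight line from zero to the end-of-infusion value lies below that curve. The area lost has the same sign in every subject, so averaging over 6 to 10 subjects does not remove it. AUC∞ of the parent is pulled down, and CL, taken as dose/AUC∞, is pushed up.

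The 6-12 h gap raises a separate question. If the parent is below the LLOQ at 12 h, the terminal fit ends at 6 h or earlier and may cover fewer than two half-lives.

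**Working it through.** **Inputs.** Protocol Table 2.4.2-1 gives AUC∞, AUCt, Cmax and half-life. By matching dose levels to Protocol 2.4.1, the single-dose rows are taken as 5-minute infusions and the multiple-dose Day 1 rows as 1-minute infusions. Assumed, because the documents do not give them: distribution half-life 0.1-0.35 h, LLOQ 1-50 ng/mL, linear kinetics, no assay noise. The SAP's AUC rule is read as linear areas, with log-down run as the alternative. The plan states no expected AUC or CL to reproduce.

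**Step 1: is the profile multi-exponential?** After a near-bolus, a one-compartment drug has Cmax/AUC∞ close to ln2/t½.

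| Row | Cmax/AUC∞ (per h) | ln2/t½ (per h) | Ratio |
|---|---|---|---|
| 7.5 mg | 1832/1242 = 1.48 | 0.59 | 2.5 |
| 15 mg | 3348/3008 = 1.11 | 0.40 | 2.8 |
| 20 mg, Day 1 | 4351/3379 = 1.29 | 0.28 | 4.7 |
| 30 mg | 7670/4882 = 1.57 | 0.41 | 3.8 |

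The table points to a fast early phase.

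**Step 2: one worked case (15 mg row, distribution half-life 0.2 h).** Rates are α = ln2/0.2 = 3.466 and β = ln2/1.73 = 0.4007 per h. Solving for the two coefficients from Cmax and AUC∞, then scaling by 16/15, gives A = 3056 and B = 932. Check: 3056/3.466 + 932/0.4007 ≈ 3209 = 3008 × 16/15.

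During a 1 h infusion C(t) = (A/α)(1 − e^(−αt)) + (B/β)(1 − e^(−βt)), so C(1) = 1622.

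- **0-1 h:** true area 1045 (33% of AUC∞); the line gives 1622/2 = 811. Error -234, or -7.3%.
- **1-6 h:** linear areas give about 1997 against 1904. Error +2.9%.
- **6-12 h:** C(6) = 103.6 and C(12) = 9.4. Linear area 6 × (103.6 + 9.4)/2 = 339 against (103.6 − 9.4)/0.4007 = 235. Error +3.2%.

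If 12 h is quantifiable, the net is -7.3 + 2.9 + 3.2 = -1.2%. If it is BLQ, the 6-12 h term drops out and the net is about -4.4% (CL about +4.6%).

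**Step 3: the same case with added samples.** C(0.5) = 1148, so the 0-1 h area becomes 287 + 692.5 = 979.5, an error of -2.0%. C(8) = 46.5, so 6-12 h becomes 150.1 + 111.7 = 261.8, an error of +0.8%. With 12 h quantifiable:

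- 0.5 h alone: -2.0 + 2.9 + 3.2 = +4.1%
- 8 h alone: -7.3 + 2.9 + 0.8 = -3.6%
- both: -2.0 + 2.9 + 0.8 = +1.7%

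**Step 4: range over the 7.5, 15, 20 and 30 mg fits.** The infusion hour holds 24-50% of AUC∞, and the single line loses about 6-11% of AUC∞.

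| AUC∞ bias | As scheduled | 0.5 h and 8 h added |
|---|---|---|
| Linear, 15 mg fit | -4.6% to +0.4% | about +0.7% to +1.8% |
| Linear, all four fits | about -10% to 0% | about -1.5% to +2% |
| Log-down, all four fits | about -13% to -5% | about -1% to -2% in most cases, -5% at worst |

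In the most extreme 30 mg case the linear result with both samples can reach about -2%, depending on which terminal points are fitted.

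**Step 5: half-life.** The last concentration implied by the table is (AUC∞ − AUCt) × ln2/t½. At 15 mg this is 140 × 0.4007 = 56.1 ng/mL. Seven computable rows from 1.25 to 30 mg give 55.5 to 63.8, which suggests an earlier assay floor near 50 ng/mL. Predicted C(12 h) is about 6-11 ng/mL (15 mg fit) or 12-26 ng/mL (20 mg fit), so 12 h would be BLQ at that floor. A 3-4-6 h fit then spans 3/1.73 = 1.7 or 3/2.51 = 1.2 half-lives; starting at 2 h, it spans 4/1.73 = 2.3 or 4/2.51 = 1.6. If 12 h is quantifiable, the span is at least 3.2 in these two fits.

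**The case against.** **The sign is not certain.** Under linear areas at the dose nearest 16 mg, the bias runs from -4.6% to +0.4%, and a one-compartment profile would reverse it (-0.1% to +7.1%). The first part stands, which is why the conclusion says likely. The second has little force, because Step 1 contradicts a one-compartment shape. A result near zero is also a cancellation of opposite errors that depends on an unstated LLOQ.

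**A reader might infer that both gaps lower AUC.** The documents do not support that. With linear areas the 6-12 h interval adds area when 12 h is quantifiable, and with log-down areas it is about neutral.

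**A reader might infer that the half-life will be unreliable.** That rests on a floor back-calculated from group means in earlier trials. The SAP also lists the span ratio and has spans below 2 discussed in the CSR. A short span would be disclosed, though not repaired.

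**Materiality.** The 15 mg AUC∞ CV is 416.6/3008 = 14%, so the standard error with 6-8 subjects is about 5-6%, as large as the likely linear-rule bias. No test or margin depends on it. This limits the consequence, but a same-direction error in a primary endpoint is still worth removing when removal is cheap.

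**Conclusion.** The missing infusion sample is a real and avoidable weakness of moderate size. AUC∞ of OPC-61815 free form is likely understated and CL overstated. With linear areas the AUC∞ bias is about -5% to 0% at the 15 mg calibration and down to about -10% with other rows. With log-down areas it is about -5% to -13%. This rests on the assumed distribution half-life and LLOQ, on kinetics carried over from 1- and 5-minute dosing, and on mean values. The effect on OPC-41061 was not quantified.

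The 6-12 h gap matters in two other ways: it can hide part of the infusion loss, and it may leave the half-life fit ending at 6 h with a span often below 2 if the LLOQ is near 50 ng/mL. Neither document settles the LLOQ. Mass balance and routes of excretion come from urine and feces and are unaffected.

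**What to change.** In Protocol Tables 1.3-1, 1.3-2 and 10.3-1, add a 0.5 h and an 8 h sample for OPC-61815 free form and OPC-41061, with sampling windows. Add them as a pair. Under linear areas, 0.5 h alone can turn the bias to about +3% to +5% when 12 h is quantifiable, and 8 h alone leaves the infusion loss in place.

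The 8 h sample is justified mainly by AUC. Its half-life benefit depends on the LLOQ: predicted C(8 h) is 32-55 ng/mL in the 15 mg fit, so it may itself be BLQ at a floor of 50, and a 4-6-8 h fit at a 2.51 h half-life spans only 4/2.51 = 1.6.

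Cost: a schedule amendment; 10 to 12 samples; 2 × 3 = 6 mL more blood (340.5 to 346.5 mL, cap 500 mL); two more draws per subject; and 16-20 extra assays for 8-10 subjects. Protocol 8.2.1 already provides for sampling from the contralateral arm by cannula. If the sponsor keeps the current times, it should state the LLOQ and whether areas are linear or log-down, and show by calculation that the schedule suffices.
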